10.2.5 Visits 6 and 7 (Days 29 and 36) Procedures

Patients should arrive at the study site having fasted for 4 to 6 hours. The following procedures will be performed at Visits 6 and 7:

Before Study Drug Administration during Visits 6 and 7:

- Record all medications (prescription and OTC) taken by the patient since previous visit
- Record all AEs since previous visit
- Record vital signs
- Perform a urine pregnancy test for all females of childbearing potential (Visit 7 only)
- Collect blood samples for:
 - CBC and chemistry
 - ESR (done at site with the kit provided)
 - CRP concentration
 - Serum SAN-300 concentration
 - Cytokine assessments (IFN_γ, TNFα, IL-6)
 - Immunophenotyping panel (CD3/CD14/CD45RO/CD49a/CD45/CD4/CD19/CD8)
 - VLA-1 receptor occupancy
- Conduct DAS28-CRP and ACR Core Set Measurements
- Complete HAQ-DI

Administer the study drug appropriate to the randomization of the patient.

After Study Drug Administration during Visits 6 and 7:

- Observe subject at minimum 1 hour post dose. Longer observation allowed if deemed necessary by investigator or designee
- Record blood pressure and pulse prior to the blood sample collection
- Collect blood samples at 1 hour post dose (Visit 7 only) for:
 - Serum SAN-300 concentration
 - Cytokine assessments (IFN_γ, TNFα, IL-6)
- Collect AEs since study drug administration

10.2.6 Visit 6A (between Days 30 to 32), Visit 7A (between Days 37 to 39), and Visit 7B (between Days 40 to 42)

Patients will come to the study site at a random, scheduled time within each of these intervals to have blood samples collected for serum SAN-300 concentration and VLA-1 receptor occupancy.

Record all AEs and medications taken since previous visit.

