- In Cohorts C and D, patients randomized to receive SAN-300 will be administered a total of three every-other-week injections of SAN-300 on Days 1, 15, and 29 and will be administered a total of three every-other-week injections of placebo on Days 8, 22, and 36.

Study assessments and measurements will be performed on Days 1, 8, 15, 22, 29, 36, and 43. Patients will also visit the clinic between study drug administration visits for the assessment of PK/PD endpoints. The primary and secondary efficacy endpoints will be assessed at the End-of-Treatment Visit on Day 43.

Follow-up Period: Days 43 to 71. Study patients will return for follow-up visits on Days 57 and 71 for safety and efficacy assessments. The Exit Visit will occur on Day 71. Patients who withdraw early from the study must return to the clinic to complete the Exit Visit assessments.

Study procedures at each visit are described in the Schedule of Assessments, provided as Appendix 2.

Amendment 5: 28 Mar 2016

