8.11 Appropriateness of Measurements

All procedures used to measure the safety, tolerability, and PK profile of SAN-300 in this study were considered by the Sponsor and Investigators to be appropriate and necessary to obtain the required safety, tolerability, and PK data for the investigational product. The safety assessments used in this study, such as vital signs, ECG, and clinical chemistry and hematology monitoring, are widely used and are considered appropriate for monitoring patient health and well-being in this type of study.

The efficacy measures were selected to be generally comparable to published clinical studies in RA. The Investigators consider the measures to be standard assessments and endpoints for this disease. CRP and ESR measurements reflect the general inflammatory state of a patient and are components of the ACR Core Set Measurements.

The PD markers were chosen to allow assessment of the immunological effects of SAN-300. These assessments are designed to provide information relevant to their usefulness as biomarkers and measures of potential safety and efficacy. Changes in VLA-1 on lymphocytes and monocytes as well as changes in the levels of the pro-inflammatory cytokines IFN γ , TNF α , and IL-6 will be useful as potential biomarkers and indications of potential efficacy. VLA-1+ leukocytes, TNF α , and IL-6 are thought to be important drivers of inflammation in RA; IFN γ is a cytokine secreted by VLA-1+ T cells. Changes (specifically, any potential increases) in the levels of IFN γ , TNF α , and IL-6 will also be important safety markers.

Amendment 5: 28 Mar 2016

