10.2.1 Visit 2 (Day 1) Procedures

Eligible patients will return to the study site for enrollment, randomization, and administration of the first dose of study drug. Patients should arrive at the study site having fasted for 4 to 6 hours. The following procedures will be performed at Visit 2:

Before Randomization:

- Review inclusion and exclusion criteria and medical history
- Record all AEs since previous visit
- Record all medications (prescription and OTC) taken by the patient since Screening
- Record RA history and prior RA treatment(s)
- Record vital signs
- Perform a urine pregnancy test for all females of childbearing potential
- Collect urine for urinalysis
- MRI of the hand and wrist most clinically affected by RA (to occur within 5 days before or at Visit 2) should be performed on patients able to tolerate the MRI procedure.

Randomize the patient via the IVRS/IWRS system.

After Randomization but before Study Drug Administration:

- Collect blood samples for:
 - CBC and chemistry
 - ESR (done at site with the kit provided)
 - International normalized ratio (INR), prothrombin time (PT), activated partial thromboplastin time (aPTT)
 - Tryptase and histamine
 - Complement (C3, C4, and CH50)
 - CRP concentration
 - Serum immunoglobulins
 - ANA
 - Anti-SAN-300 antibodies
 - Serum SAN-300 concentration
 - Cytokine assessments (IFN_γ, TNFα, IL-6)
 - Immunophenotyping panel (CD3/CD14/CD45RO/CD49a/CD45/CD4/CD19/CD8)
 - VLA-1 receptor occupancy
- Conduct the DAS28-CRP and ACR Core Set Measurements
- Complete the HAQ-DI

Administer study drug according to the randomization of the patient. Day 1 study drug administration should occur on the day of or within 24 hours after randomization.

After Study Drug Administration:

 Observe subject at minimum 1 hour post dose. Longer observation allowed if deemed necessary by investigator or designee.

Amendment 5: 28 Mar 2016

 Record blood pressure and pulse at the end of the 1 hour observation period prior to the blood sample collection

- Collect blood sample at 1 hour post dose for serum SAN-300 concentration
- Collect AEs since study drug administration

10.2.2 Visit 2A (between Days 2 to 4) and Visit 2B (between Days 5 to 7)

Patients will come to the study site at a random, scheduled time within each of these intervals to have blood samples collected for serum SAN-300 concentration and VLA-1 receptor occupancy.

Record all AEs and medications taken since previous visit

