10.2.3 Visits 3, 4, and 5 (Days 8, 15, and 22) Procedures

Patients should arrive at the study site having fasted for 4 to 6 hours. The following procedures will be performed at Visits 3 to 5:

- Record all medications (prescription and OTC) taken by the patient since previous visit
- Record all AEs since previous visit
- Record vital signs
- Perform a urine pregnancy test for all females of childbearing potential (Visit 5 only)
- Collect blood samples for:
 - CBC and chemistry
 - ESR (done at site with the kit provided)
 - CRP concentration
 - Anti-SAN-300 antibodies (Visit 3 only)
 - Serum SAN-300 concentration
 - Cytokine assessments (IFN_γ, TNFα, IL-6) (Visit 3 only)
 - Immunophenotyping panel (CD3/CD14/CD45RO/CD49a/CD45/CD4/CD19/CD8) (Visits 3 and 4 only)
 - VLA-1 receptor occupancy (Visits 3 and 4 only)
- Conduct the DAS28-CRP and ACR Core Set Measurements
- Administer the study drug appropriate to the randomization of the patient
- Complete the HAQ-DI
- Observe subject at minimum 1 hour post dose. Longer observation allowed if deemed necessary by investigator or designee
- Record blood pressure and pulse at the end of the 1 hour observation period
- Collect AEs since study drug administration

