10.2.7 Visit 8: End-of-Treatment Visit (Day 43) or Early Withdrawal Visit (Treatment Period)

Patients should arrive at the study site having fasted for 4 to 6 hours. The following procedures will be performed at the End-of-Treatment Visit (Visit 8) or at an Early Termination Visit for patients who discontinue study participation during the Treatment Period:

Amendment 5: 28 Mar 2016

Record all medications (prescription and OTC) taken by the patient since Visit 7

- Record all AEs since previous visit
- Perform a 12-lead ECG
- Perform a physical examination
- Record vital signs
- Collect urine for urinalysis
- Perform a serum pregnancy test for all females of childbearing potential
- Collect blood samples for:
 - CBC and chemistry
 - ESR (done at site with the kit provided)
 - INR, PT, aPTT
 - Complement (C3, C4, and CH50)
 - CRP concentration
 - Serum immunoglobulins
 - Anti-SAN-300 antibodies
 - Serum SAN-300 concentration
 - Cytokine assessments (IFN_γ, TNFα, IL-6)
 - Immunophenotyping panel (CD3/CD14/CD45RO/CD49a/CD45/CD4/CD19/CD8)
 - VLA-1 receptor occupancy
 - RF, ANA, and ACPA
- Conduct DAS28-CRP and ACR Core Set Measurements
- HAQ-DI
- MRI of the hand and wrist most clinically affected by RA (same as screening) should be performed on patients who are able to tolerate the MRI procedure.

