Appendix 3 Specialty PK and PD Laboratory Testing Schedule

For all cohorts, blood samples for PK and PD analysis will be collected at the specified times predose and postdose, at random times intermittently scheduled between dosing visits, and at visits within the Follow-up Period. A predose sample will be collected before every study drug administration. A postdose sample will be collected at 1 h after the first study drug administration on Day 1 and at 1 h after the last study drug administration on Day 36. In addition, all patients will return to the study site at random times within the specified intervals between certain study drug administration visits for additional sample collection. Finally, samples will be collected for all cohorts after the end of all drug dosing, on Days 43, 50, and 64.

SC Dose #:	SC #1				SC #2		SC #3	SC #4	SC #5		SC #6				End-of- Treat- ment Visit	Per	ow-up
Week:		VV	k 1		V\	/k 2	Wk 3	Wk 4	VV	k 5		V	Vk 6		Wk 7	WK 8	Wk 10
Visit:	V	isit 2	Visit 2A	Visit 2B	Visit 3	Visit 3A	Visit 4	Visit 5	Visit 6	Visit 6A	Vis	sit 7	Visit 7A	Visit 7B	Visit 8	Visit 8A	Visit 9A
Day:	Day 1	Day 1	Day 2-4	Day 5-7	Day 8	Day 9-11	Day 15	Day 22	Day 29	Day 30-32	Day 36	Day 36	Day 37-39	Day 40-42	Day 43	Day 50	Day 64
Timing:	Pre- Dose	1 h Post- Dose	Random	Random	Pre- Dose	Random	Pre- Dose	Pre- Dose	Pre- Dose	Random	Pre- Dose	1 h Post- Dose	Random	Random			
PK	Х	Х	Х	Х	Х	Х	Х	Х	Х	Х	Х	Х	Х	Х	Х	Х	Χ
Cyto	Х				Х				Х		Х	Х			Х		
RO	Х		Х	Х	Х		Х		Х	Х	Х		Х	Х	Х	Х	Χ
IPT	Х				Х		Х		Х		Х				Х	Х	Х
ADA	Х				Х										Х		Х

Abbreviations: ADA = anti-drug (SAN-300) antibody; Cyto = cytokines (IFNγ, TNFα, IL-6); IPT = immunophenotyping panel (CD3, CD4, CD8, CD45, CD45RO, CD14, CD19, and CD49α); PK = pharmacokinetics; RO = receptor occupancy (VLA-1); SC = subcutaneous. Note: At each visit, AEs and medications taken should be recorded.

Santarus, Inc. CONFIDENTIAL SAN-300 Clinical Trial Protocol: C2013-0302

Amendment 5: 28 Mar 2016

Page 67 of 118

ACR / EULAR RA Classification Criteria Appendix 4

ACR / EULAR RA Classification Criteria (2010)

Target population (Who should be tested?):

- 1. Patients who have at least one joint with definite clinical synovitis (swelling)¹
- 2. Patients whose synovitis is not better explained by another disease²

Classification criteria for RA (score-based algorithm: add score of categories A–D; a score of ≥ 6/10 is needed for classification of a patient as having definite RA)3

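### Acute cytokine change cannot be assessed after the first dose in any cohort, or after any active dose in the every-other-week cohorts (C and D)

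*Protocol*

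**What the plan says.** Protocol 8.11 says of increases in the three cytokines that they "will also be important safety markers". Safety is the primary objective (Protocol 2.1).

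The Appendix 3 grid marks cytokines six times: before dosing on Days 1, 8, 29 and 36, 1 h after the Day 36 injection, and on Day 43. The visit sections (10.2.1, 10.2.3, 10.2.5 and 10.2.7) agree. For the 1 h sample, 10.2.5 reads "Collect blood samples at 1 hour post dose (Visit 7 only) for" SAN-300 concentration and cytokines. The Appendix 3 lead-in places the second post-dose sample "at 1 h after the last study drug administration on Day 36".

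Two nearby draws omit cytokines. On Day 1 the instruction is "Collect blood sample at 1 hour post dose for serum SAN-300 concentration". At Visits 2A and 2B (Days 2 to 7) patients have "blood samples collected for serum SAN-300 concentration and VLA-1 receptor occupancy".

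Protocol 3.1 gives SAN-300 patients in Cohorts C and D active injections on Days 1, 15 and 29, and "three every-other-week injections of placebo on Days 8, 22, and 36". In Cohorts A, B, E and F all six weekly injections are active.

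**The concern.** If increases in these cytokines are to inform safety, a reader will expect some view of what happens soon after exposure, above all first exposure. The schedule gives none before Day 8. Its one early sample comes late in treatment and, in two of the planned cohorts, follows a placebo injection.

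Protocol 11.7 summarises pharmacodynamic parameters by time point and treatment group. A Day 36 1 h column for the every-other-week SAN-300 arms would therefore look like an acute response to SAN-300 at 2.0 and 4.0 mg/kg, when it is a value 7 nominal days after the last active dose. A flat result there could be taken as evidence of no acute cytokine release, although no sample capable of showing one was scheduled.

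**Working it through.** There is no plan figure to reproduce. The check crosses the cytokine sampling times with the active-dose days.

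Inputs:
- Cytokine times: Appendix 3 grid and Protocol 10.2.1 to 10.2.7.
- Active-dose days: Protocol 3.1. Cohorts A, B, E, F: Days 1, 8, 15, 22, 29, 36. Cohorts C, D: Days 1, 15, 29.
- Six SAN-300 patients per cohort: Protocol Table 2.
- Visit window of ±2 days: Protocol 10.2.

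Formula: time since last active dose = sample day − day of the most recent SAN-300 injection. A pre-dose sample does not count that day's injection.

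| Cytokine sample | A, B, E, F | C, D |
|---|---|---|
| Day 1 pre-dose | baseline | baseline |
| Day 8 pre-dose | 8 − 1 = 7 d | 8 − 1 = 7 d |
| Day 29 pre-dose | 29 − 22 = 7 d | 29 − 15 = 14 d |
| Day 36 pre-dose | 36 − 29 = 7 d | 36 − 29 = 7 d |
| Day 36, 1 h post-dose | 1 h | 36 − 29 = 7 d (1 h after placebo) |
| Day 43 | 43 − 36 = 7 d | 43 − 29 = 14 d |

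Results:
- In A, B, E and F, 1 of 6 active doses (the sixth) has a cytokine sample scheduled earlier than nominal 7 days.
- In C and D, 0 of 3 active doses has one.
- Patients affected: 6 + 6 = 12. With Cohort F, 12/36 = 33%. Without it, 12/30 = 40%. The remaining 24 of 36 (18 of 30) have one early sample, after the last dose only.

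The days are nominal. With the window, the Day 8 sample can fall 6 − 1 = 5 to 10 − 1 = 9 days after the first dose. If both visits move, the Day 36 sample in C and D can fall 34 − 31 = 3 to 38 − 27 = 11 days after the Day 29 dose. An early-withdrawal visit (10.2.7) also takes cytokines and could come sooner, but it is not a scheduled time point.

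Two sets of passages disagree:
- Protocol 8.7 has pharmacodynamic samples, cytokines included, drawn together with the PK samples, and the Appendix 3 lead-in describes a Day 1 1 h sample under a combined PK and PD heading. The grid and 10.2.1 assign that draw to SAN-300 concentration only.
- Footnote c of Protocol Appendix 2 and of SAP Appendix 1 names Cohorts C and E as every other week, where the body text has C and D. On the footnote's allocation the affected pair is C and E, again 6 + 6 = 12 patients.

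**The case against.** Section 8.11 speaks of increases without mentioning post-dose timing. Cytokines are listed as pharmacodynamic parameters, and SAP 2.2.2 does not name them among the safety endpoints. Acute clinical safety is watched in other ways: at least 1 h of observation with blood pressure and pulse after each injection, adverse events recorded at Visits 2A and 2B, and tryptase and histamine in suspected hypersensitivity. The documents give no cytokine kinetics, so nothing shows that 1 h after a subcutaneous injection is an informative time. All of this stands, and it limits the weight of the point. It does not restore a sample that was not scheduled, and the protocol itself chose a 1 h cytokine sample, which in two cohorts follows placebo.

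The misreading described above is a risk and not a planned analysis. Treatment groups are displayed by cohort, so C and D would not be merged with the weekly arms. The value could still be misread within its own column. Neither the protocol nor the SAP says how to label it, and the separate population PK/PD plan was not available to check.

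SAP 3.5 reports that 41 subjects were randomised, so schedule changes may come too late for this trial. Labelling and a stated limitation remain possible.

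**Conclusion.** The point stands as a gap in acute cytokine sampling: no assessment soon after the first dose in any cohort, and none soon after any active dose for the 12 SAN-300 patients in the every-other-week cohorts. No cytokine sample is scheduled earlier than nominal 7 days in either case.

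Three stronger readings are tempting, and the documents do not support them:
- That patients have no cytokine sample after the first dose. All are scheduled for samples on Days 8, 29, 36 and 43.
- That cytokine increases cannot be assessed at all. Sustained or trough rises can be compared with Day 1 and with pooled placebo in every cohort, and a 1 h change after the sixth dose can be assessed in A, B, E and F.
- That the Day 36 1 h PK sample is equally compromised. The planned population model can use a concentration 7 days after dosing, and C and D have PK samples after active doses at Day 1 1 h, Visits 2A and 2B, and Visit 6A.

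The conclusion assumes the body-text allocation of regimens, nominal visit days and full cohorts of six. It makes no claim that a cytokine rise is expected or that 1 h is the best time to look.

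**What to change.** - **Protocol 10.2.1 and Appendix 3:** add cytokines to the existing 1 h draw on Day 1, and optionally to the existing Visit 2A draw. For the Day 1 cytokine sample this also brings the grid into line with 8.7 and the Appendix 3 lead-in.
- **Protocol 10.2.5 and Appendix 3:** in the every-other-week cohorts, take the later 1 h cytokine sample at Visit 6 (Day 29) instead of Visit 7, for all patients including placebo, so that timing does not reveal assignment.
- **Data already collected:** label the Day 36 1 h cytokine value in the every-other-week SAN-300 arms 'post-placebo injection', do not interpret it as an acute response to SAN-300, and state the limitation in the report.
- **Regimen allocation:** reconcile footnote c of Protocol Appendix 2 and SAP Appendix 1 with the body text.

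Cost: one or two extra cytokine assays per patient on draws already made. The Day 29 sample replaces the Day 36 one, but Visit 6 has no post-dose draw now. It therefore adds a blood draw there if the PK sample stays on Day 36, at a visit where patients are already observed for 1 h. The pooled placebo group's later 1 h sample would fall on Day 29 in some cohorts and Day 36 in others. Tabulating it as '1 h after last active-schedule injection' handles that.

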10.2.7 Visit 8: End-of-Treatment Visit (Day 43) or Early Withdrawal Visit (Treatment Period)

Patients should arrive at the study site having fasted for 4 to 6 hours. The following procedures will be performed at the End-of-Treatment Visit (Visit 8) or at an Early Termination Visit for patients who discontinue study participation during the Treatment Period:

Amendment 5: 28 Mar 2016

Record all medications (prescription and OTC) taken by the patient since Visit 7

- Record all AEs since previous visit
- Perform a 12-lead ECG
- Perform a physical examination
- Record vital signs
- Collect urine for urinalysis
- Perform a serum pregnancy test for all females of childbearing potential
- Collect blood samples for:
 - CBC and chemistry
 - ESR (done at site with the kit provided)
 - INR, PT, aPTT
 - Complement (C3, C4, and CH50)
 - CRP concentration
 - Serum immunoglobulins
 - Anti-SAN-300 antibodies
 - Serum SAN-300 concentration
 - Cytokine assessments (IFN_γ, TNFα, IL-6)
 - Immunophenotyping panel (CD3/CD14/CD45RO/CD49a/CD45/CD4/CD19/CD8)
 - VLA-1 receptor occupancy
 - RF, ANA, and ACPA
- Conduct DAS28-CRP and ACR Core Set Measurements
- HAQ-DI
- MRI of the hand and wrist most clinically affected by RA (same as screening) should be performed on patients who are able to tolerate the MRI procedure.

10.3 Follow-up Period (Days 43 to 71)

10.3.1 Visit 8A (Day 50) and Visit 9A (Day 64)

Patients will come to the study site to have blood samples collected for:

- Serum SAN-300 concentration
- VLA-1 receptor occupancy
- Immunophenotyping panel
- Anti-SAN antibodies (Visit 9A only)
- Record all AEs and medications taken since previous visit

10.3.2 Visit 9 (Day 57) and Visit 10 (Day 71) or Early Withdrawal Visit (Follow-up Period)

Patients should arrive at the study site having fasted for 4 to 6 hours. The following procedures will be performed at Visits 9 and 10 or at the Early Termination Visit for patients who discontinue study participation during the Follow-up Period:

Record all medications (prescription and OTC) taken by the patient since previous visit

Santarus, Inc.
SAN-300
Confidential
Clinical Trial Protocol: C2013-0302

Amendment 5: 28 Mar 2016

- Record all AEs since previous visit
- Perform a physical examination (Visit 10 and Early Termination only)
- Record vital signs
- Collect urine for urinalysis (Visit 10 and Early Termination only)
- Collect blood samples for:
 - CBC and chemistry
 - ESR (done at site with the kit provided)
 - INR, PT, aPTT (Visit 10 and Early Termination only)
 - Complement (C3, C4, and CH50) (Visit 10 and Early Termination only)
 - CRP concentration
 - Serum immunoglobulins (Visit 10 and Early Termination only)
- Conduct DAS28-CRP and ACR Core Set Measurements
- Complete the HAQ-DI

Amendment 5: 28 Mar 2016

11 PLANNED STATISTICAL METHODS

11.1 General Considerations

All endpoints in this study will be summarized by descriptive statistics. Descriptive statistics for continuous variables will include the mean, standard deviation, median, first and third quartiles, minimum, and maximum value; categorical variables will be presented as counts and percentages. All statistical tests will be conducted at the two-sided $\alpha = 0.05$ level of significance. All tests of binomial proportions will be conducted using the chi-square test unless more than one cell in a 2 x 2 table has an expected value of < 5, in which case the Fisher's Exact Test will be used. All tests of continuous variables will be conducted using the Wilcoxon Rank-Sum Test. For all efficacy endpoints, patients will be analyzed according to the treatment to which they were randomized. For all safety endpoints, patients will be analyzed according to the treatment they received. Parameters presented by "treatment group" will compare the 6 patients on SAN-300 from each cohort with the 10 pooled patients on placebo.

11.2 Determination of Sample Size

There is no sample size calculation, as this study is not intended to be powered to demonstrate efficacy. Results from this study will be used to design future efficacy studies.

11.3 Analysis Populations

11.3.1 Intent-to-Treat Population

The Intent-to-Treat (ITT) Population is defined as all randomized patients who received at least one dose of a study drug. Patients in the ITT Population will be analyzed according to the treatment to which they were randomized.

The ITT Population is the primary population for the analysis of all efficacy endpoints.

